## **2.4 Summary of Study Design**

This is a Phase 2b, open-label, non-randomized, single-arm study to evaluate the safety, and efficacy of HBI-8000 40 mg BIW in patients with relapsed or refractory ATL (R/R ATL). Study patients will ingest HBI-8000 approximately 30 minutes after any regular meal BIW. There will be 3 to 4 days between dosing. A treatment cycle is defined as 28 consecutive days. HBI-8000 administration will be continued until PD or the occurrence of unacceptable toxicities despite optimal supportive care.

Response and progression for ATL will be evaluated according to the criteria of the International Consensus Meeting [Tsukasaki 2009] (see [Appendix D](#)).

#### **2.4.1 Safety Determination and Criteria for Dose Modification or Interruption**

National Cancer Institute Common Terminology Criteria for Adverse Events (NCI CTCAE) version 4.03 will be used to grade the severity of toxicities. Abnormalities of laboratory tests (investigation) must be evaluated for clinical significance. Study treatment may be held, and dose may be reduced in the event of unacceptable toxicities. (See [Section 2.6.8](#) for Guidelines.)

### **2.5 Selection of Study Population**

#### **2.5.1 Inclusion Criteria**

Patients may be entered in the study only if they meet **all** of the following criteria:

1. Histopathological, or cytological diagnosis of ATL confirmed as seropositive for anti-Human T-lymphotropic Virus type-I (HTLV-I) antibody
2. Acute, lymphoma or unfavorable chronic types. The unfavorable chronic type is defined by the presence of at least 1 of the following: serum albumin <3.5 g/dL, lactic dehydrogenase (LDH) >300 U/L or blood urea nitrogen (BUN) >25 mg/dL. The patient must have at least 1 of measurable lesion, or evaluable lesion in either of peripheral blood or skin.
3. Relapsed or refractory disease after receiving prior systemic therapy with mogamulizumab, or  $\geq 1$  prior systemic therapy with cytotoxic chemotherapy in case of intolerance/contraindication for mogamulizumab. And there is no other standard treatment which can be considered appropriate for patients.
4. Male or female, aged 20 years or older
5. Eastern Cooperative Oncology Group (ECOG) Performance Status of 0 to 2
6. Life expectancy of greater than 3 months
7. Meeting the following baseline laboratory criteria for screening:
  - a. Absolute Neutrophil Count >1500/ $\mu$ L independent of growth factor support within 7 days
  - b. Platelets >75,000/ $\mu$ L independent of transfusion within 14 days
  - c. Hemoglobin >8 g/dL independent of transfusion within 14 days
  - d. Serum creatinine <1.5  $\times$  upper limit of normal (ULN)
  - e. Serum aspartate aminotransferase/glutamyl oxaloacetic transaminase (AST/SGOT) and alanine aminotransferase/glutamyl pyruvic transaminase (ALT/SGPT)  $\leq 3 \times$  ULN
  - f. Serum bilirubin  $\leq 1.5 \times$  ULN
8. Negative serum pregnancy test for females of childbearing (reproductive) potential. Female patients of child bearing potential must use an effective method of birth control (e.g., hormonal contraceptive, intrauterine device, diaphragm with spermicide or condom with spermicide) during treatment period and 1 month thereafter. Males must use an effective method of birth control (2 barrier methods) during treatment period and 3 months thereafter.

Note: Female patients will be considered to be women of childbearing potential unless having undergone permanent contraception or postmenopausal. Postmenopausal is defined as at least 12 months without menses with no other medical reasons (e.g., chemical menopause because of treatment with anti-malignant tumor agents).

9. Signed informed consent

**2.5.2 Exclusion Criteria:**

Patients who meet **any** of the following criteria are **not** to be enrolled:

1. Patients in whom central nervous system lymphoma is recognized during screening (if suspected clinically, imaging study should be performed to confirm)
2. Male patients with QTcF >450 msec at screening, female patients with QTcF >470 msec at screening, or patients with congenital long QT syndrome, clinically significant arrhythmia, history of congestive heart failure (New York Heart Association Class III or IV) or acute myocardial infarction within 6 months of starting the study drug at screening.
3. Patients with known hypersensitivity to benzamide class of compounds or any of the components of HBI-8000 tablets, and patients with prior exposure of HBI-8000
4. Patients with a history of second malignancy other than disease under study. The exceptions are diseases (excluding diseases listed below) that have been treated with curative intent with no evidence of recurrence in past 5 years. Furthermore, if the second malignancy is one of the following diseases that were treated with curative intent, it is only required that there is no evidence of recurrence in past 2 years:
  - a. Basal cell carcinoma of the skin
  - b. Squamous cell carcinoma of the skin
  - c. Cervical carcinoma in situ
  - d. Carcinoma in situ of the breast
  - e. An incidental histological finding of prostate carcinoma (TNM Stage T1a or T1b)
  - f. Early-stage gastric cancer treated with endoscopic mucosal resection or endoscopic submucosal dissection
5. Autologous stem cell transplantation within 12 weeks (84 days) of starting the study drug
6. History of allogeneic stem cell transplantation
7. Organ transplantation recipients except autologous hematopoietic stem cell transplantation
8. Uncontrolled intercurrent infection
9. Hepatitis B surface antigen-positive, or hepatitis C virus antibody positive. In case hepatitis B core antibody and/or hepatitis B surface antibody is positive even if hepatitis B surface antigen negative, a hepatitis B virus DNA test (real-time polymerase chain reaction measurement) should be performed and if positive, the patient should be excluded from study
10. Any history of testing positive for human immunodeficiency virus or known acquired immunodeficiency syndrome
11. Uncontrolled diabetes mellitus, hypertension, endocrine disorder, bleeding disorder
12. Major surgery or radiation therapy within 28 days of starting the study drug

13. Receiving investigational agents or anti-cancer therapy within 28 days, nitrosourea or mitomycin C within 42 days, of starting the study drug
14. Receiving antibody therapy for ATL within 4 weeks of starting the study drug
15. Women who are breastfeeding or women who are not willing to stop breastfeeding during study treatment period and for 30 days after the last dose of study drug
16. Potential for non-compliance or at increased risk based on investigator's judgement

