### 2.6.1 Screening Assessments (within 28 days prior to start of treatment)

Written informed consent for participation in the study must be obtained before performing any study specific screening tests or evaluations. Informed Consent Forms (ICFs) for all patients screened (whether enrolled or not) will be maintained at the study site.

All screening and baseline assessments must be completed and reviewed to confirm that patients meet all eligibility criteria. An Eligibility Screening Form documenting the investigator's assessment of each screened patient with regard to the protocol's inclusion and exclusion criteria is to be completed and kept at the study site.

Screening assessments include medical history and concomitant medications, documentation of ATL diagnosis in accordance with the WHO revised classification [WHO 2008] and treatment history. Screening assessments will be performed within 28 days prior to Cycle 1 Day 1 (C1D1). A pretreatment bone marrow test (aspiration or biopsy) would be required. Results of standard-of-care tests or examinations performed prior to obtaining informed consent and within 28 days prior to C1D1 may be used (and do not need to be repeated for screening unless they do not meet the criteria defined in the protocol). Similarly, tumor assessment tests <2 weeks outside the 28-day window in the absence of clinical evidence of PD, the results may be accepted.

Women of childbearing potential must agree to practice contraceptive measures after signing informed consent. A negative serum pregnancy test will be obtained during screening.

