### **2.10.1 Prohibited Medications and Therapy**

The following drugs are prohibited.

- Drugs known to produce significant QT prolongation and ventricular dysrhythmias (see [Appendix E](#))  
Prohibited from signing informed consent through the EoT assessment
- Anti-cancer therapy other than study medication

Prohibited during the study and within the following time intervals prior to the first dose of study drug.

- 4 weeks for anti-cancer chemotherapy
- 6 weeks for nitrosourea and mitomycin C
- 4 weeks for anti-cancer monoclonal antibody therapy

Corticosteroid prescribed for medical conditions other than lymphoma is not considered as an anti-cancer therapy for this study, for example: chronic obstructive pulmonary disease for allergy, topical steroids for rash.

-Please note that patient use of any prohibited medication is considered a protocol violation. In the event of prohibited medication use, investigator should consult study medical monitor to define an appropriate course of action if needed.

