#### **9.4.2.1.4      Definition of Measurable Lesion (common with nodal and extranodal lesion)**

In evaluable lesions, measurable lesion is defined as the lesion that meets both following criteria:

- The size by Long dimension over 1.5 cm on sectional image of CT
- Definitely measurable by 2 orthogonal dimensions (long dimension and its orthogonal dimension) on sectional image of CT

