#### **9.4.2.1.6      Selection of target lesions**

Target lesions are selected from measurable lesions, which can be nodal lesion and extranodal lesion, along with the following criteria:

- Lesions that is suitable to be measured exactly and continuously by the same method should be selected
- Lesions are selected up to 6 in descending order by long dimension size on sectional image of CT. If measurable lesions are less than 6, all measurable lesions are selected

The lengths of long dimension (cm) and short dimension (cm) which is orthogonal to long dimension are measured, and their product (2-dimension product:  $\text{cm}^2$ ) will be calculated.

The sum of all 2-dimension products ( $\text{cm}^2$ ) will be calculated and defined as the sum of 2-dimension products at screening.

2-dimension product of each target lesion ( $\text{cm}^2$ ) = long dimension (cm)  $\times$  short dimension (cm) which is orthogonal to long dimension

The sum of 2-dimension products at screening = 2-dimension product (target lesion 1) + 2-dimension product (target lesion 6)

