##### 9.4.3.1.1 Evaluation of target lesion

Efficacy for target lesion will be assessed by calculating reduction rate (A) and growth rate (B) of the sum of 2-dimension products according to the following formula:

$$(A) = \frac{(C) \text{ at screening} - (C) \text{ at evaluation}}{(C) \text{ at screening}} \times 100$$

$$(B) = \frac{(C) \text{ at evaluation} - \text{minimum } (C)}{\text{minimum } (C)^{*1}} \times 100$$

\*1: minimum (C) value obtained during the study including the screening

(C) = sum of 2-dimension products

Criteria for assessment of anti-tumor effect on target lesion are as follows:

CR: Absence of enlarged lymph node, AND disappearance of all extranodal lesions.

CRu: Reduction rate of the sum of 2-dimension products of  $\geq 75\%$ , but presence of residual lesion

PR: Reduction rate of the sum of 2-dimension products of  $\geq 50\%$  and  $< 75\%$

SD: Effect not reached PR, but not PD

PD: Growth rate of the sum of 2-dimension products of  $\geq 50\%$

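### Shrinkage from radiotherapy given before day -28 can count toward an HBI-8000 response, because the baseline scan may fall just after or even before it and target selection has no rule for irradiated lesions

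*Combined protocol and SAP*

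**What the plan says.** **Before dosing.** Criterion 12 in Section 2.5.2 excludes "Major surgery or radiation therapy within 28 days of starting the study drug". Criterion 13 sets a general limit with the same anchor: "Receiving investigational agents or anti-cancer therapy within 28 days, nitrosourea or mitomycin C within 42 days, of starting the study drug". Radiotherapy that ended before day -28 is therefore compatible with entry.

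**On study.** Section 2.10.1 prohibits "Anti-cancer therapy other than study medication". Radiotherapy is not named there, but the wording would ordinarily cover it.

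**Baseline scan.** Section 2.6.1 sets a 28-day screening window. It also lets a tumor assessment less than 2 weeks outside that window stand, provided there is no clinical evidence of progression.

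**Target lesions.** Section 9.4.2.1.6 has a suitability condition, "Lesions that is suitable to be measured exactly and continuously by the same method should be selected", and a size rule, "Lesions are selected up to 6 in descending order by long dimension size on sectional image of CT". With fewer than 6 measurable lesions, all of them are targets. Section 9.4.2.1.4 defines measurability by size and two dimensions only.

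**Response.** Section 9.4.3.1.1 states: "Efficacy for target lesion will be assessed by calculating reduction rate (A) and growth rate (B) of the sum of 2-dimension products". Reduction is taken from screening: 50% up to 75% is PR, and 75% or more with residual lesion is CRu.

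The lesion definitions, skin rules, response rules and independent-review sections (3.4.2, 3.4.3) do not mention prior irradiation.

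**The concern.** The washout protects the interval from radiotherapy to first dose. Response, however, is measured from the baseline scan, and nothing ties that scan to the radiotherapy. A lesion still shrinking from radiation, or scanned before it was irradiated, can enter the target sum, and the later reduction is scored without regard to cause.

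The trial has one arm, and its main analysis is meant for regulatory submission (Section 5.1). ORR is set against a 5% rate in 18 evaluable patients (Section 5.2), with no control arm to show how many responses would have occurred without the drug. At that size a single misattributed response can decide whether 5% is excluded.

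**Working it through.** **Step 1. Timing routes that the text allows**

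| Route | Baseline scan | Radiotherapy | Criterion 12 | What is credited to the drug |
|---|---|---|---|---|
| A | day -28 | ends day -29 | met | only shrinkage occurring after the scan |
| B | about day -41 (28 days plus just under 14) | between the scan and day -29 | met | the whole radiation effect, since baseline precedes it |

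Route B is the stronger. The absence of clinical progression required by Section 2.6.1 does not rule it out.

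**Step 2. When one lesion is enough for a target-lesion PR**

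Let w be the irradiated lesion's share of the screening sum and r its fractional shrinkage, with other lesions unchanged. Then reduction rate (A) = w × r × 100. PR needs w × r ≥ 0.50, and CRu needs w × r ≥ 0.75. Even if the lesion vanishes (r = 1), its share must be at least 50% for PR or 75% for CRu.

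Example with assumed sizes: an irradiated lesion of 4 × 3 = 12 cm² and an untreated one of 3 × 2 = 6 cm², sum 18 cm². If the first shrinks to 3 cm² (r = 0.75, w = 12/18), the sum is 9 cm² and the reduction is (18 − 9)/18 = 50%. That meets the target-lesion PR threshold with no drug effect. Overall PR under Table 8 also requires at least a 50% decrease in involved skin and blood, and no increase in spleen or liver.

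**Step 3. The plan's own figure**

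Inputs from Section 5.2: comparison rate 5%, target 30%, 5% two-sided alpha, n = 18, power 80%. The exact binomial upper tail is held to 2.5%.

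- P(X ≥ 3 | 18, 0.05) = 5.8%, too large.
- P(X ≥ 4 | 18, 0.05) = 1.1%, so the implied rule is 4 or more responders.
- P(X ≥ 4 | 18, 0.30) = 83.5%. With 17 patients it is 79.8%, so 18 agrees with a power of at least 80%.

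The exact 95% intervals agree: 3/18 gives 3.6% to 41.4% (5% not excluded), and 4/18 gives 6.4% to 47.6% (excluded).

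**Step 4. Sensitivity to miscounted responses**

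Let s be the assumed share of drug non-responders scored as responders because of radiotherapy. At a true 5% rate the observed rate is p = 0.05 + 0.95 × s.

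| s (assumed) | p | P(X ≥ 4 of 18) |
|---|---|---|
| 0 | 0.0500 | 1.1% |
| 1% | 0.0595 | 2.0% |
| 1.5% | 0.06425 | 2.5% (0.0252) |
| 2% | 0.0690 | 3.2% |
| 5% | 0.0975 | 9.1% |

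Stated as counts: if exactly one of the 18 is miscounted, success needs 3 or more of the other 17, with probability 5.0%. If exactly two are, it needs 2 or more of 16, with probability 18.9%.

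**The case against.** The strongest reply is that this is a corner case. In Route A, a scan nearer to first dose already contains much of the radiation effect, so only late shrinkage is credited. Route B needs a scan reused from outside the normal window. In acute or unfavorable chronic disease, skin or blood may also have to respond. The documents give no rate of recent radiotherapy, and the 4-of-18 rule has slack: at 1% miscounting the error is still 2.0%. Treatment history is collected at screening, and independent oncologists see clinical data as well as scans. Response follows cited consensus criteria, and Section 5.1 leaves detailed methods to a SAP whose text is not available here. All of this limits the size and likelihood of the problem. None of it supplies a rule, since the independent reviewers are told only to apply the same criteria.

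Three stronger readings are tempting and are not supported:

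- That radiotherapy is unrestricted once treatment starts. The general ban in Section 2.10.1 speaks against this; the gap concerns radiotherapy before day -28.
- That an irradiated lesion by itself yields an overall PR. Step 2 and Table 8 show that this holds only when the lesion dominates the sum and other involved compartments qualify.
- That the false-positive rate is in fact above nominal. It depends on a miscounting rate that the documents do not give.

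It is also fair that recent systemic therapy has the same washout anchor. That is a wider question and does not remove this one.

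**Conclusion.** The concern holds as a gap in the measurement rules. As written, they can score radiation shrinkage as part of a PR or CRu, and nothing in the available text lets a reader or an independent reviewer set it aside. The direction of the bias in ORR is upward.

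Its size is unknown. With 18 evaluable patients, the implied 4-responder rule and a true rate of 5%, the error stays under 2.5% up to roughly 1.5% miscounting of non-responders, and is 3.2% at 2% and 9.1% at 5%. These rates are assumptions, not estimates. The sample size is unaffected. The change is worth making because it is cheap and one response can decide the result.

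**What to change.** 1. **Section 9.4.2.1.6.** State that a lesion in a previously irradiated field may be a target lesion only if imaging shows growth since the radiotherapy. Otherwise follow it as a non-target lesion under the existing grades in 9.4.3.1.2 or 9.4.3.1.3, outside reduction rate (A).
2. **Section 2.6.1.** Do not accept a screening tumor assessment that predates the last radiotherapy. This closes Route B.
3. **eCRF, independent review and analysis.** Record radiotherapy site and date, and give them to the independent radiologists and oncologists. Report an ORR sensitivity analysis that counts responses resting on irradiated lesions as non-responses, including irradiated skin scored by mSWAT, which item 1 does not reach.

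Leave inclusion criterion 2 and the length of the washout unchanged.

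Cost: two short text changes, eCRF fields and one extra analysis. Showing growth since radiotherapy needs earlier images where they exist. A few patients will have fewer target lesions, and a rare patient will need a baseline scan inside the normal window where an older one would have been reused.

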## 2.6 Study Procedures Overview

Patients may be treated in this study as long as they receive clinical benefit (SD or a response) in the absence of unacceptable toxicity. Progressive disease would be determined by investigators based on local radiology findings and clinical judgement. No independent radiology review is required prior to designation of PD and treatment discontinuation. Independent Radiology Review and Independent Overall Efficacy Review will be performed for final efficacy analyses at the completion of this study.

To ensure patient safety, a data safety monitoring board (DSMB) will convene to review the cumulative safety profiles of study patients at following milestones: first 6 patients completing at least 1 cycle, 12, 18, 30 patients have been treated for at least 1 cycle; and at end of treatment (EoT) phase of the study. Based on the observed safety, dose and regimen of ongoing treatment may be modified as needed. For all patients, weekly safety laboratory tests will be obtained during the first 28 days and closely monitored for safety signals, especially the neutropenia and transaminase elevation.

It is estimated that each patient will be on study for up to 12 months after enrollment. Assuming that 24 months are needed to meet accrual target, the study period would be of 36 months to allow efficacy and safety determination. After study drug is discontinued, patients will be followed as described in [Sections 2.6.4](#) and [2.6.5](#).

Patients will be screened by the study site investigator prior to entry into the study. Patients will receive a detailed explanation of the study design, and the potential risk/benefit of treatment will be disclosed to patients prior to the screening process. Only eligible and consenting patients will be enrolled in the study. The investigator will maintain a screening log to record all patients screened.

Local radiology reports on disease status will guide investigator's decision on-study treatment, including discontinuation. At the end of the study, tumor response of each patient will be reviewed by independent radiologists and oncologists in a blinded fashion to obtain best response, dates of response and progression. The data from independent and local assessment will be analyzed in parallel in final study report.

The Schedule of Events is presented in [Table 4](#) of [Appendix A](#) (Section 9.1).

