## **2.6.9 Management and Dosage Modifications for Non-Hematologic Adverse Events**

In the event of Grade 3 non-hematologic AEs (excluding isolated abnormality of laboratory values not associated with clinical significance), study medication should be held. Appropriate treatment should be initiated. Patients will be closely monitored for recovery and managed following the Dose Adjustment Guideline. If the AEs recur despite 2 dose reductions as applicable, study treatment should be discontinued. Study treatment should be terminated if Grade 4 non-hematologic adverse events occur, following the Dose Adjustment Guideline (Table 1).

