## **3.4 Independent Review**

### **3.4.1 Data Safety Monitoring Board**

A DSMB has been established to monitor the safety observed during the conduct of this study. For all patients, weekly safety laboratory tests should be obtained during the first 28 days and closely monitored for safety signals, especially the neutropenia and transaminase elevation. DSMB consists of 3 oncologists who are experienced in treating patients with ATL and are not associated with this study. They are assisted by 1 DSMB statistician.

DSMB convenes at planned intervals based on patient accrual (see [Section 2.6](#)). Upon reviewing cumulative safety data from the study and taking into consideration of state-of-the-art medical practice, they will advise sponsor for treatment modification including dose adjustment, AE management, and continuation of treatment.

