### **5.2 Determination of Sample Size**

For efficacy determination, 18 patients evaluable for efficacy per protocol criteria are required. To ensure meeting this target, 22 patients would be enrolled if 20% of patients are assumed not to complete required study treatment or evaluations for efficacy determination. Enrolled patients will be treated with the starting dose of 40 mg BIW to provide an assessment of tumor response as well as additional safety data.

The target best ORR for this study is 30%, on the basis of the ORR results that were obtained in study TG0902CDM. The power for showing the response rate >5% at 5% two-sided alpha in 18 patients is 80%.

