## 9.0 APPENDICES

### 9.1 Appendix A: HBI-8000-210 Schedule of Events

**Table 4: Schedule of Events**

	Screening	Cycle 1				Cycle 2		Cycle $\geq 3$ a	EoT b	Survival F/U c
DAY	-28 to 0	1	8 ± 2	15 ± 2	22 ± 2	1 ± 4	15 ± 4	1 ± 7		
		Pre-dose d	3.5 hrs			Pre-dose	3.5 hrs		Pre-dose	
HBI-8000 d,e		BIW f				BIW f		BIW f		
Written informed consent	X									
Medical history, diagnosis and treatment history, demographics, height	X									
Physical examination, weight	X	X		X		X		X	X	
ECOG Performance Status	X	X				X			X	X
Vital signs g	X	X		X		X		X	X	
12 Lead ECG (Safety)	X							X	X	
12 Lead ECG (QTc) h		X	X			X	X			
Hematology i	X	X		X	X	X		X	X	
Coagulation j	X	X		X		X			X	
Chemistry k	X	X		X	X	X		X	X	
Urinalysis l	X	X								X
Hepatitis B/C virus, and HTLV-I Antibody tests m	X									
Serum pregnancy test (if applicable) n	X	X							X	
Tumor assessment o	X					X		X o	X o	X o
Patient survival; new cancer therapies										X
Adverse events assessment	X	X		X	X	X		X	X	X
Concomitant medication	X	X		X	X	X		X	X	X

Abbreviations: ALT, alanine aminotransferase; aPTT, activated partial thromboplastin time; AST, aspartate aminotransferase; BIW, twice weekly; BUN, blood urea nitrogen; ECG, electrocardiogram; ECOG, Eastern Cooperative Oncology Group; EoT, end of treatment; F/U, follow-up; GGT, gamma-glutamyl transpeptidase; INR, international normalized ratio; LDH, lactate dehydrogenase; mSWAT, Modified Severity-Weighted Assessment Tool; PCR, polymerase chain reaction; PT, prothrombin time;

- a Cycle/Day designation is based on actual calendar days after the first dose. All visits and assessments may be performed  $\pm$  7 days to accommodate unforeseen delays, holidays, or vacations.
- b “End of Treatment” visit should be conducted  $30 \pm 3$  days after the last dosing of the study drug, or before the initiation of new cancer treatment, whichever is earlier.
- c Survival data will be collected every 3 months  $\pm$  2 weeks after EoT until death or the end of the study, defined as 12 months after the administration of the last dose of the entire study.
- d On the days of scheduled visits that is the same as the dosing scheduled day, patient should take study drug after receiving confirmation from investigator to continue study treatment.

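### The count-based DSMB reviews wait for patients who get through Cycle 1, so deaths and permanent stops in Cycle 1 do not advance the count, and Section 3.4.1 describes a different count

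*Combined protocol and SAP*

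**What the plan says.** Section 2.6 states that a DSMB "will convene to review the cumulative safety profiles of study patients" at set milestones: "first 6 patients completing at least 1 cycle, 12, 18, 30 patients have been treated for at least 1 cycle". The same sentence adds one further review, "and at end of treatment (EoT) phase of the study".

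Section 3.4.1 refers back to Section 2.6 but describes the timing differently: "DSMB convenes at planned intervals based on patient accrual".

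Three other provisions bear on the count:

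- Section 2.4: "A treatment cycle is defined as 28 consecutive days". Note a to Table 4 adds: "Cycle/Day designation is based on actual calendar days after the first dose".
- Section 2.6.9: "Study treatment should be terminated if Grade 4 non-hematologic adverse events occur". Table 1 also ends treatment when recovery from the listed events takes more than 2 weeks.
- Sections 2.6.6 and 5.4: Cycle 1 withdrawals are replaced unless they are due to drug toxicity or progression.

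On numbers, Section 5.2 says "22 patients would be enrolled if 20% of patients are assumed not to complete required study treatment", and Section 2.6 allows 24 months for accrual.

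**The concern.** A trigger that counts only patients who get through Cycle 1 leaves out those whose experience an early safety review most needs to weigh: patients who die or come off drug permanently in the first 28 days. The more such patients there are, the more must be dosed before the board first meets. The DSMB is the independent body that advises the sponsor on dose adjustment and on continuing treatment. The protocol states no event-triggered DSMB meeting, no enrolment pause and no DSMB stopping rule, so during accrual the milestones alone fix when the board meets.

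Section 3.4.1 makes the intention uncertain. Accrual and Cycle 1 completion are different counts, and the text does not say which governs.

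**Working it through.** **Inputs**

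- Milestones m = 6, 12, 18 (Section 2.6). The 30-patient milestone exceeds the planned enrolment of 22 and is a separate matter.
- Cycle length 28 days (Section 2.4), or 28/30.4 = 0.92 months.
- Enrolment 22 (Section 5.2) over 24 months (Section 2.6). If uniform, 22/24 = 0.92 patients per month.
- q, the share who die or permanently stop before Day 28. The documents do not give it, so 10%, 20% and 33% are assumed.

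**The plan's own figure.** Inflating 18 by 20% gives 18 × 1.2 = 21.6, so 22, as stated. Dividing instead gives 18/0.8 = 22.5, so 23. The difference does not matter here, and 22 is used.

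**Who advances the count, read literally**

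| Patient | Section 2.6 count | Accrual count (3.4.1) |
|---|---|---|
| On study at Day 28 | yes | yes |
| Dose held in Cycle 1, still on study at Day 28 | yes, because cycle days are calendar days | yes |
| Permanent stop before Day 28 for toxicity | no | yes |
| Permanent stop before Day 28 for progression | no | yes |
| Death before Day 28 | no | yes |

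The calendar-day note is attached to the Cycle ≥3 column of Table 4, but its wording is general and it is applied here to Cycle 1.

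**Formulas**

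- Expected patients dosed to obtain m completers: m/(1 − q). For m = 6: 6/0.90 = 6.7, 6/0.80 = 7.5, 6/0.67 = 9.0.
- Expected months to the review: [m/(1 − q)]/(22/24) + 0.92. For m = 6 and q = 20%: 7.5/0.917 + 0.92 = 9.1.
- Chance of reaching m completers among 22 dosed with no replacement: P(X ≥ m), X binomial (22, 1 − q).

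**Results**

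| q | Dosed to reach 6 | Months to 6 / 12 / 18 | P(12 reached in 22) | P(18 reached in 22) |
|---|---|---|---|---|
| 0% | 6.0 | 7.5 / 14.0 / 20.6 | 100% | 100% |
| 10% | 6.7 | 8.2 / 15.5 / 22.7 | over 99% | 94% |
| 20% | 7.5 | 9.1 / 17.3 / 25.5 | over 99% | 54% |
| 33% | 9.0 | 10.7 / 20.5 / 30.2 | 93% | 10% |

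Accrual plus one cycle ends at 24 + 0.92 = 24.9 months. The entries 25.5 and 30.2 therefore mean that the 18-patient review is not expected within 22 patients.

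Under either count, a few patients may also start during the 28 days in which the last counted patient is followed: about 0.92 × 0.92 = 0.8 patients.

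**With early stops counted.** Every dosed patient eventually counts, so the 6-, 12- and 18-patient reviews fall at about 7.5, 14.0 and 20.6 months whatever q is.

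**The case against.** The strongest reply is that this is loose wording with little practical effect. Several parts of it stand.

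- Section 3.4.1 points to Section 2.6 and speaks of accrual, so the sponsor may have meant the first 6 patients once their Cycle 1 period is over. That is possible, but the text does not say it. Section 5.5.2 expressly adds Cycle 1 progression stops to the per-protocol set, and the DSMB trigger has no such clause.
- The delay to the first review is modest: 9.1 − 7.5 = 1.6 months at 20% and 10.7 − 7.5 = 3.2 months at 33%. Accrual of about one patient a month staggers exposure in any case.
- The 20% in Section 5.2 covers failure to complete treatment or efficacy evaluations. It is neither a Cycle 1 rate nor a toxicity rate. Section 1.8 reports Grade 3 and 4 toxicity in 2 of 6 Phase 1 patients at 40 mg, described as transient, which does not support a 33% rate of permanent stops.
- Cycle 1 withdrawals for other reasons are replaced, so a calculation fixed at 22 with no replacement is a worst case for those losses.
- Weekly Cycle 1 laboratory tests, SAE entry within 24 hours (Section 3.2.7.1) and study discontinuation on safety information (Section 2.6.7) are real safeguards. None is stated to convene the DSMB.

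A reader might go further and infer that every DSMB review depends on completers, that any rise in toxicity delays review, or that the board never sees early stoppers' data. The documents support none of these. A review is also scheduled at the end of the treatment phase. Toxicity managed by a hold leaves the count unchanged if the patient is still on study at Day 28, while early progression delays it just as a toxicity stop does. Each review covers cumulative data.

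**Conclusion.** The concern holds as a matter of timing. Followed literally, Section 2.6 makes the count-based reviews later as deaths and permanent Cycle 1 stops become more frequent, from toxicity or progression alike, and Section 3.4.1 gives a different basis for the same meetings. The end-of-treatment-phase review does not help while patients are still being enrolled.

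For the first review the effect is small to moderate: 6.7, 7.5 or 9.0 patients dosed instead of 6 at assumed stopping rates of 10%, 20% and 33%. It is larger for the 18-patient review, the last count-based one that 22 patients can reach, with a chance of about 94%, 54% and 10%. These figures assume independent stops at a constant rate, and the last three also assume 22 dosed with no replacement. The months assume uniform accrual. The rates are illustrative, since the documents give none. The case for change rests on the counting rule and the conflict between the two sections, not on any one of these rates.

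**What to change.** In Section 2.6, define the count for the DSMB milestones as patients who have received at least 1 dose of HBI-8000 and have either completed Cycle 1 or discontinued during it for any reason, including death. Align Section 3.4.1 to the same count. Keep the end-of-treatment-phase review as it is. Resolve the 30-patient milestone explicitly as a separate point, so that it is neither dropped silently nor left unreachable.

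The cost is about one sentence in each section. The reviews at 6, 12 and 18 remain, and come earlier only if Cycle 1 losses are frequent. The small downside is that some counted patients contribute less than 28 days of data. No dose or treatment rule changes.
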